### 9.3.5 Efficacy analysis (mITT Population)

In general, the need for rituximab rescue will be considered “treatment failure” for the analysis of efficacy endpoints except cumulative CS and composite GTI score.

The analyses for efficacy endpoints involving clinical assessment of CR during the blinded treatment period will be performed based on data collected during on-site visits (i.e., not including data collected from remote visits) as the primary analyses.

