### Other analyses:

For analyses of following parameter,

- Change in PDAI score from baseline to Weeks 5, 13, 25, 37 and 61
- Total number of disease flares/relapses from initial CDA to Week 37
- Glucocorticoid Toxicity Index (GTI) score at Week 37
- Change in Autoimmune Bullous Disease Quality of Life (ABQOL) score from baseline to Weeks 5, 13, 25, 37, and 61

- Change in EuroQOL-5 Dimension 5 Level (EQ-5D-5L) results (visual analog scale [VAS] results and individual dimension) scores from Baseline to Weeks 5, 13, 25, 37 and 61.

If a patient receives a rituximab therapy, the study data up to the date of the first dose of rituximab (but not including data from the date of the first dose of rituximab) will be included in the analyses.

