**Other responder analysis:**

- Proportion of patients with ABQOL Score of zero at Weeks 5, 13, 25, 37, and 61 the patient will be counted as a non-responder starting from the date of first dose of rituximab for the responder analysis.

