### 8.3. Other Secondary Analyses

The following endpoints will be analyzed in a manner similar to that described for the primary endpoint in Section 8.1, with exception of the additional subgroup analyses described in Section 6.1.3.2:

- The proportion of patients who are in CR from Week 29 to Week 37 with a CS dose of  $\leq 5$  mg/day
- The proportion of patients who have a PDAI score  $< 3$  from Week 29 to Week 37 with CS  $\leq 10$  mg/day

Cumulative duration of CR with a CS dose  $\leq 10$  mg/day from Baseline to Week 61; cumulative duration of CR with a zero CS dose from Baseline to Week 61 and the cumulative duration of CR with a zero CS dose from Week 37 to Week 61 will be analyzed based on the same methods described for the cumulative duration of CR with CS dose  $\leq 10$ mg/day from Baseline to Week 37.

Change from baseline to Weeks 5, 13, 25, 37, and 61 in PDAI will be analyzed using restricted maximum likelihood (REML)-based mixed model for repeated measures (MMRM) with fixed effects for treatment, week, baseline PDAI and treatment by week interaction. For the analysis of the differences at Weeks 5, 13, 25, and 37, only all data up to Week 37 will be included in the model. For the analyses of the difference at 61 weeks, only data collected during the Open-Label Extension Period will be included in the model (from Week 39 onward). A contrast will be written within the MMRM model to get each Week-specific treatment difference (least squares treatment means, treatment difference estimates and 95% CIs). ABQOL and EQ-5D-5L overall VAS scores will be analyzed similarly.

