Descriptive summaries presenting the raw scores and change from baseline will be presented for ABQOL, PDAI, and EQ-5D-5L and EQ-5DVAS scores by treatment group at each study visit. Additionally, descriptive summaries for responses to the EQ-5D-5L dimensions of mobility, self-care, usual activities, pain/discomfort, and anxiety/depression will be displayed as frequency counts by category and treatment group for each study visit (Week 37, as well as Weeks 5, 13, 25 and 61). Results will be analyzed using a CMH test, stratified by disease history. The observed number and proportion of subjects reporting No Problems, as well as the resulting Mantel-Haenszel risk difference (PRN1008 – placebo), estimated SE, 95% CI and the associated p-value will be reported. Descriptive summaries will be presented separately for the blinded treatment, open label, and long term extension periods of the study.

The proportion of patients with 3 or more lesions within 1 month or extension of established lesions that do not heal spontaneously within 1 week from Baseline to Week 37 will be analyzed using the same methodology as the primary endpoint as described in Section 8.1. The total number of disease flares/relapses from initial CDA to Week 37 will be analyzed based on the same methodology described for the cumulative duration of CR with CS dose  $\leq$  10mg/day from Baseline to Week 37 in Section 8.2.

A Kaplan Meier analysis will be used to estimate the median and other quartiles for Time to first flare/relapse from initial CDA to Week 37, along with two-sided 95% confidence intervals. The number of events and censored observations will be presented as well as graphical representations of estimated survival curves. A hazard ratio for treatment comparisons will be presented, along with its 95% confidence interval, based on a Cox regression model with terms for treatment group and disease history. The endpoint will be evaluated based on a p-value from a log-rank test stratified by disease history for treatment group comparison.

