## 10. Changes from Planned Analysis

Not applicable.

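### SAP 6.1.5.2 cuts PDAI, ABQOL and EQ-5D data at first rituximab with no failure value, an undeclared departure from Protocol 9.3.5; EQ-5D and ABQOL-zero then treat rescued patients differently

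*SAP*

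**What the plan says.** Protocol 9.3.5 states that, in general, "the need for rituximab rescue will be considered" treatment failure "for the analysis of efficacy endpoints except cumulative CS and composite GTI score". PDAI, ABQOL and EQ-5D are not among the exceptions.

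SAP 6.1.5.2, under Other analyses, takes a different route for change in PDAI, ABQOL and EQ-5D-5L (VAS and individual dimensions). In a patient given rituximab, it includes "the study data up to the date of the first dose of rituximab (but not including data from the date of the first dose". No value is assigned after that date. The same list holds GTI and the number of flares, which are not pursued here.

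The next paragraph of 6.1.5.2 handles ABQOL score of zero by a failure rule: "the patient will be counted as a non-responder starting from the date of first dose of rituximab for the responder analysis".

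SAP 8.3 sets the analyses:
- **Change in PDAI:** a "restricted maximum likelihood (REML)-based mixed model for repeated measures (MMRM) with fixed effects for treatment, week, baseline PDAI and treatment by week interaction", with ABQOL and EQ VAS treated similarly. For Weeks 5 to 37, "only all data up to Week 37 will be included in the model". For Week 61, only open-label data from Week 39 onward enter.
- **EQ-5D dimensions:** a CMH test stratified by disease history, by visit. "The observed number and proportion of subjects reporting No Problems, as well as the resulting Mantel-Haenszel risk difference" will be reported.

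SAP 10, on changes from the planned analysis, reads "Not applicable". The change table in SAP 2.2 does not list the rescue rule either.

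**The concern.** Rescued patients stay on trial and blinded (Protocol 4.1), and PDAI and quality of life are scheduled at Week 37. Their later data are therefore collected and then set aside. Under Appendix 1 of the protocol, rituximab follows a second flare with PDAI at or above the higher of the Screening and Day 1 scores, or failure to reach disease control on high-dose or maximally tolerated corticosteroid. The excluded data therefore follow a poor clinical course.

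Three things are at stake:
- The analysis answers a different question from the one in Protocol 9.3.5, and the SAP does not say so.
- Two quality-of-life proportions in the same report treat the same rescued patient in opposite ways.
- No sensitivity analysis of the rescue rule is planned for these endpoints, so a reader could not tell whether it matters.

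**Working it through.** The documents give no rescue rate and no expected result for these endpoints, so there is no plan figure to reproduce. All rates and effects below are assumptions.

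**1. EQ-5D dimensions, Week 37.** Let pA and pB be the No Problems proportions among non-rescued patients (active, placebo), and rA and rB the rescue proportions.
- Exclusion: pA − pB
- Rescue as failure: pA(1 − rA) − pB(1 − rB)
- Failure minus exclusion: pB·rB − pA·rA

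With pA = 40% and pB = 25%, exclusion gives 15.0 points throughout.

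| Rescue active/placebo | Rescue as failure | Difference (points) |
|---|---|---|
| 5%/10% | 0.380 − 0.225 | 15.5 |
| 5%/15% | 0.380 − 0.2125 | 16.8 |
| 5%/20% | 0.380 − 0.200 | 18.0 |
| 10%/10% | 0.360 − 0.225 | 13.5 |
| 10%/15% | 0.360 − 0.2125 | 14.8 |

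Exclusion understates the difference only if rB/rA exceeds pA/pB, here 0.40/0.25 = 1.6. With pA = 50% and pB = 35%, exclusion again gives 15.0. Failure counting gives 0.475 − 0.2975 = 17.8 at 5%/15%, 0.475 − 0.280 = 19.5 at 5%/20%, and 0.450 − 0.315 = 13.5 at 10%/10%.

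**2. Mixed models, Weeks 5 to 37.** A simulation used 60,000 patients per arm to remove sampling noise. It assumed PDAI change at Weeks 5, 13, 25 and 37, SD 12, correlation 0.75 to the power of the visit lag, a drug effect of −3 at Week 37, and rescue given to patients with the worst scores. The likelihood analysis used is equivalent to an MMRM for data missing from one visit onward. In the kept case, the score that triggers rescue is in the model. In the left-out case, it is not. The failure column scores rescued patients as no change from baseline, a value chosen for illustration.

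| Rescue active/placebo | Trigger score | No-rescue truth | Observed cases | MMRM | Failure = 0 change |
|---|---|---|---|---|---|
| 10%/20% | kept | −3.01 | −1.79 | −3.04 | −3.39 |
| 10%/20% | left out | −2.90 | −1.25 | −1.83 | −3.00 |
| 10%/30% | kept | −3.01 | −0.54 | −3.02 | −4.29 |
| 10%/30% | left out | −3.01 | +0.24 | −0.90 | −3.84 |
| 30%/10% | kept | −2.92 | −5.37 | −2.89 | −0.45 |
| 30%/10% | left out | −3.16 | −6.39 | −5.27 | −1.10 |
| 10%/10% | kept | −3.08 | −3.08 | −3.07 | −2.77 |
| 10%/10% | left out | −2.97 | −2.94 | −2.95 | −2.65 |

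With the trigger score kept, the MMRM recovers the no-rescue difference. With it left out and rescue unequal between arms, the MMRM is biased in favour of the arm with more rescue. The SAP allows this to happen in two ways. Section 6.1.5.2 excludes an assessment made on the rituximab date itself, and 6.1.6 uses an unscheduled assessment only if no scheduled one is available.

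**3. Week 61 model.** It uses data from Week 39 onward. A patient rescued in the blinded period has no usable data after first rituximab, so contributes nothing.

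**The case against.** A reader might infer that the comparison drops the worst patients and so hides benefit. The documents do not support that in three respects.
- For the Week 5 to 37 models, data are cut but patients are not removed. Earlier visits stay in, normally including the first qualifying flare, and the model can recover the no-rescue difference.
- The direction is not fixed. At 10%/10% rescue, exclusion gives the larger EQ-5D difference, and with more rescue on rilzabrutinib the drug effect can be overstated.
- Rescued patients are not shown to be the worst in the trial. Under Appendix 1, life-threatening flares lead to stopping study drug and conventional immunosuppression, and the lack-of-control route to rituximab has no PDAI threshold.

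The conflict is also softer than a flat contradiction. Protocol 9.3.5 says in general, and Protocol 9.3.6 itself prescribes mixed models for change scores. Neither document defines failure for a change score. The protocol lets the SAP modify plans and makes it the final authority. Cutting data at rescue is a recognised way to target the outcome without rescue. All of this stands. It makes the truncated MMRM defensible, but not undeclared: the protocol synopsis asks the SAP to address changes of substance, and named exceptions that omit these endpoints leave little room for an unstated one. Protocol 9.3.10 leaves missing data to the SAP, but these data are observed and then excluded.

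Finally, the SAP does not state the EQ-5D denominator. Exclusion is inferred from 6.1.5.2 read with a by-visit CMH test. No imputation rule for the dimensions appears in the visible text, so this is the natural reading.

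**Conclusion.** The point holds in a limited form. SAP 6.1.5.2 departs from the general failure rule in Protocol 9.3.5 for PDAI, ABQOL and EQ-5D, and does not declare it.

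The firmest part is the inconsistency between the EQ-5D No Problems proportion and ABQOL-zero. Over the assumed rates, the choice moves the EQ-5D difference from 15.0 points to between 13.5 and 19.5, in either direction.

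For the Week 5 to 37 models, the target is the outcome without rescue. If rescue depends on scores that are in the model, that target is estimated without material bias. The risk of bias arises where the relapse score is left out and rescue differs by arm. In the Week 61 model, patients rescued in the blinded period are absent altogether.

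These endpoints lie outside the testing hierarchy and SAP 6.1.4 calls them exploratory, so the primary and key secondary tests are unaffected.

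**What to change.** 1. In SAP 6.1.5.2, move the EQ-5D dimension No Problems analysis to the rule already used for ABQOL-zero: not No Problems from the date of first rituximab.
2. For change in PDAI, ABQOL and EQ VAS, keep the truncated MMRM but state that it targets the outcome without rescue, and that the Week 61 model has no data from patients rescued in the blinded period. Retain the last assessment before or on the date of first rituximab, including an unscheduled relapse assessment, as an exception to 6.1.5.2 and 6.1.6. Add a sensitivity analysis with a prespecified failure score from first rituximab onward, for example the worse of baseline and the last pre-rituximab value. That score is a proposal; the protocol contains none.
3. Declare the departure from Protocol 9.3.5 in SAP 10.

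The cost is SAP wording, programming and one extra table per endpoint. No data collection changes.

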**Other responder analysis:**

- Proportion of patients with ABQOL Score of zero at Weeks 5, 13, 25, 37, and 61 the patient will be counted as a non-responder starting from the date of first dose of rituximab for the responder analysis.

**6.1.6. Analysis Visit Windows**

For all analyses presented by study week, unscheduled and/or repeated measurements will only be included if a scheduled measurement is not available and the unscheduled/repeated measurement falls within the analysis visit windows as described below (Table 2 and Table 3). Otherwise, visits will be analyzed as scheduled.

**Table 2: Analysis Visit Windows – Blinded Treatment Period**

Analysis Visit Name	Target Day of Planned Visit	Assessment Window (Days)
Week 3	15	Post-dose – Day 21
Week 5	29	22 – 42
Week 9	57	43 – 70
Week 13	85	71 – 98
Week 17	113	99 – 126
Week 21	141	127 – 154
Week 25	169	155 – 182
Week 29	197	183 – 210
Week 33	225	211 – 238
Week 37	253	239 – Pre-open label dose

If more than 1 visit occurs within a single visit window, then the analysis will use the visit closest to the target day. If 2 visits within the same visit window are equidistant from the target day, then the analysis will use the later visit.

**Table 3: Analysis Visit Windows – Open-Label and Long Term Period Extension Periods**

Analysis Visit Name	Target Day of Planned Visit	Assessment Window (Days)
Week 39	267	Post-open label dose – 273
Week 41	281	274 – 294
Week 45	309	295 – 322
Week 49	337	323 – 350
Week 53	365	351 – 378
Week 57	393	379 – 406
Week 61	421	407 – Pre-long term extension dose
Week 65	449	Post-long term extension dose - 462
Week 69	477	463 – 490
Week 73	505	491 - 546
Week 85	589	547 - 630
Week 97	673	631 - 714
Week 109	757	715 - 770

### 6.1.7. Pooling of Sites

Data from all investigative sites will be pooled for all planned analyses. Analysis of individual site findings will be considered if necessary.

### 6.1.8. Derived Variables

Variables associated with primary or key efficacy analyses will be derived based on data imputed as identified in Section 6.1.5.

- Time from Pemphigus diagnosis to enrollment (years) = (screening date - first date of pemphigus diagnosis +1)/365.25
- Duration calculations are generally produced as: end date – start date + 1.

**Table 4: Event and Censoring Details for Time to First CR with a CS dose at or below 10 mg/day**

Situation	Date of First CR/ Date of Censoring	Censored/ Event
No post baseline assessments	Date of first dose	Censored
Patient in CR status and with a CS dose of $\leq 10$ mg/day	First date that patient is in CR status and with a CS dose of $\leq 10$ mg/day as identified in Section 6.1.9.	Event
Rituximab administered	Date of first Rituximab administration	Censored
No CR with a CS dose of $\leq 10$ mg/day during the Blinded Treatment Period	Date of last efficacy assessment during blinded treatment phase (through Week 37)	Censored
Study discontinuation	Date of last efficacy assessment prior to or on the date of treatment discontinuation	Censored
Death before CR	Date of death	Censored

Note: Patients will be censored prior to a CR event at the earliest date of the censored events above should a censoring reason occur. Censoring reasons may be categorized for reporting (eg, by discontinuation reason).

- Three or more lesions within 1 month that do not heal spontaneously within 1 week or extension of established lesions = Yes if any of the following conditions are satisfied:
  - eCRF entry “Have new lesions appeared within a month that did not heal spontaneously within 1 week? OR Have there been extension of established lesions?” = Yes for any visits from Baseline up to Week 37.
  - At this visit, Has a Relapse occurred or is continuing?

The number of instances with investigator assessments of disease worsening will also be derived and categorized for reporting as 0, 1, 2, and  $\geq 3$ . After the first worsening, a patient can have additional worsening, but only after the patient returns to CDA first, and then the next worsening can happen.

- PDAI score  $< 3$  from Week 29 to Week 37 with a CS dose of  $\leq 10$  mg/day = Yes if the following conditions are both satisfied:
  - PDAI  $< 3$  = Yes for all visits from Week 29 through Week 37
  - Daily prednisone dose is  $\leq 10$  mg/day from Week 29 through Week 37 as defined in Section 6.1.9.
  - No Rituximab therapy prior to Week 37.

After applying the CS dose imputation as described in Section 6.1.5.2, a patient with partial missing data (missing PDAI assessment or CS dose) or complete missing data at any scheduled visit will be considered as a non-responder.

- Change from baseline = value at current time point – value at Baseline.
- PDAI Total Score = the Total PDAI activity score as reported on the PDAI Total Score CRF (possible range of 0 to 250) as the sum of the individual skin activity, scalp activity and mucosal activity scores, higher score corresponding to worsening.
- PDAI activity subscores for skin (range 0 to 120), scalp (range from 0 to 10) and mucosal (range from 0 to 120)
- ABQOL Score of zero, = Yes if zero; = No if ABQOL is present and nonzero; missing otherwise.
- TABQOL = Sum of the 17 items of the ABQOL Questionnaire. Each item is scored on a scale of 0-3 for each of the 4 options (all the time, sometimes, occasionally and never), with 0 being the least severe and 3 being the most severe. No imputation will be done for missing item, therefore the total score will be missing if any item is missing.
- EQ-5D-5L: The EQ-5D-5L comprises the EQ-5D 5 dimensions (mobility, self-care, usual activities, pain/discomfort and anxiety/depression) and a visual analogue scale (VAS).

Each dimension has 5 levels: no problems, slight problems, moderate problems, severe problems and extreme problems. Overall health state is then defined as a 5-digit number. The health utility index value will be calculated using the crosswalk value sets provided in the EQ-5D-5L Index Value Calculator created by the EuroQol Group and using mapping function developed by Van Hout et al.. The values sets based on UK population will be used for all countries. The health utility score will be missing if response to one or more dimension is missing.

- The EQ VAS records the respondent’s self-rated health on a 20 cm vertical VAS with endpoints labelled 0 (‘the worst health you can imagine’) to 100 (‘the best health you can imagine’). This information can be used as a quantitative measure of health as judged by the individual respondents. EQ VAS will be described as given by patient. Missing data will not be imputed.
- At least one relapse/flare after initial CDA to Week 37 = Yes if the following condition is satisfied:
  - eCRF entry “At this visit, Has a Relapse occurred or is continuing?” = Yes for any visits from CDA to Week 37.
  - If a patient received a rituximab dose prior to Week 37, the patient will be counted as Yes.

Relapse/flare can only happen following an initial CDA, subjects never achieve CDA prior to Week 37 will not be included in analysis. After the first initial flare, a patient can have additional relapse/flare, but only after the patient returns to CDA first, and then the next relapse/flare can happen. A similar method will be used to identify the number of relapses/flare from Week 37 to Week 61.

- Time to initial flare/relapse after initial CDA: Outcomes and durations for specific cases will be based on [Table 5](#). The date of the event/censoring is considered the end date and the date of initial CDA is considered the start date, for duration calculations.

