### **Visit Scheduling:**

The goal is to complete the visit with all associated assessments in its entirety, even if this occurs late and out of window. If the visit is delayed for multiple weeks and rolls over into the next scheduled visit period, the previous visit will be considered missed and the subject should continue with that next scheduled protocol visit.

Aim to return the patient to the original visit schedule, based on the randomization date and Suvoda visit schedule.

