## 8.2. Key Secondary Efficacy Analyses

The key secondary endpoint of Cumulative CS dose from baseline to Week 37, adjusted for time to study discontinuation will be calculated using the summation of the CS data as described in Section 6.1.9 and will be analyzed using an ANCOVA model with terms for treatment group and disease history. The estimated mean difference in cumulative CS usage (PRN1008 minus

placebo) and the associated 95% CI will be reported. Missing data for this endpoint is described in Section 6.1.5.2. The “time to study discontinuation” covariate is up to study discontinuation, first Rituximab administration if any, or the end of the blinded treatment period whichever happens first.

If outliers or skewed data is present, sensitivity analysis will be conducted on this secondary endpoint of average weekly CS usage over 36 weeks in which the data will be rank-transformed prior to analysis.

Cumulative CS dose from Week 37 to Week 61 will be analyzed similarly.

Cumulative duration of CR with CS dose  $\leq 10$ mg/day from Baseline to Week 37, will be based on a zero-inflated negative binomial model with terms for treatment group and disease history. The p-value and estimated treatment difference (parameter difference of PRN1008 minus placebo) from the negative binomial component will be reported, along with the 95% CI for the estimated parameter. The difference estimate will also be back-transformed (e.g. exponentiated) to demonstrate the relative difference in the number of pemphigus free days between treatment groups. Cumulative duration of CR with CS dose  $\leq 10$ mg/day from Baseline to Week 37 will also be summarized based on descriptive statistics.

A Kaplan Meier analysis will be used to estimate the median and other quartiles for Time (Days) to first CR with a dose of  $\leq 10$  mg/day, along with two-sided 95% confidence intervals. The number of events and censored observations will be presented as well as graphical representations of estimated survival curves. A hazard ratio for treatment comparisons will be presented, along with its 95% confidence interval, based on a Cox regression model with terms for treatment group and disease history. The endpoint will be evaluated based on a p-value from a log-rank test stratified by disease history for treatment group comparison. In addition, a landmark analysis will be done at Week 37 in the key secondary analysis and at Week 61 for the other secondary analysis.

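### Time to first CR: censoring completers on their own Week 37 visit date biases the Kaplan-Meier curve inside the Week 37 visit window, so the tail and any quartile or landmark read there are unreliable

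*SAP*

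**What the plan says.** SAP Table 4 dates the event at the "First date that patient is in CR status and with a CS dose of" at most 10 mg/day, with the dose as derived under Section 6.1.9. A patient with no such event in the blinded period is censored at the "Date of last efficacy assessment during blinded treatment phase (through Week 37". For someone who completes the period, that is the Week 37 visit.

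Times run on actual dates: "Duration calculations are generally produced as: end date – start date + 1" (SAP 6.1.8). Week 37 has target Day 253. The protocol's blinded-period schedule allows ±3 days, which is Days 250 to 256. The SAP analysis window is wider, "239 – Pre-open label dose" (SAP Table 2). Protocol Appendix 9A also accepts late visits: "The goal is to complete the visit with all associated assessments in its entirety, even if this occurs late and out of window".

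SAP 8.2 then plans these summaries: "A Kaplan Meier analysis will be used to estimate the median and other quartiles for Time (Days) to first CR", the survival curves, a Cox hazard ratio, and "a landmark analysis will be done at Week 37 in the key secondary analysis", with no method or reading day for the landmark. The formal test is separate: "The endpoint will be evaluated based on a p-value from a log-rank test stratified by disease history for treatment group comparison".

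**The concern.** At Week 37 the same examination decides both outcomes. A clear patient has an event that day and an uncleared patient is censored that day. A patient examined on Day 250 without CR is dropped before the events of Day 251 are counted, although both patients had the same visit. Each later day in the window therefore sets its events against a smaller risk set. At earlier scheduled visits, uncleared patients who continue stay at risk, so this does not arise for them.

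Nothing in the visible text realigns the times. The windowing rule in SAP 6.1.6 is for analyses presented by study week, and there is no common end date or interval-censored method.

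This is the third key secondary endpoint. With complete follow-up, the Kaplan-Meier estimate at the end of the period should equal the plain proportion with a first CR by Week 37. Under Table 4 it would not. An arm could even be given a median time to remission although fewer than half of its patients remitted.

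**Working it through.** The documents state no event rate, median or power for this endpoint, so there is no planned figure to reproduce.

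**Inputs from the documents:** actual-date events and censoring (SAP Table 4, 6.1.8); target Day 253 (SAP Table 2); ±3 days (protocol schedule for the blinded period); about 60 patients per arm and about 45 per arm with PV (protocol, Study Population, with 1:1 allocation).

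**Assumptions, because the documents are silent:** true CR by Week 37 of F = 15%, 30%, 50% or 70%; a share s = 5%, 10% or 20% of first CRs appearing at the Week 37 visit; visits spread evenly over the seven days; no drop-out; every such event dated on the visit day.

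**Step 1: hazard in the window.** Let q be the risk of first CR at Week 37 among patients still event-free. On the first day one seventh of them are seen, so the hazard is q/7. Those patients then leave, and the next day's hazard is q/6, and so on down to q/1.
- Sum over the window: q × (1/7 + 1/6 + 1/5 + 1/4 + 1/3 + 1/2 + 1) = 2.59q, where q would be right.
- Sum to Day 253: q × (1/7 + 1/6 + 1/5 + 1/4) = 0.76q.
- For q = 10%, the product of (1 − 0.10/k) for k = 1 to 7 is 0.765. That is a drop of 23.5% instead of 10%. To Day 253 (k = 4 to 7) the drop is 7.4%.

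**Step 2: effect on the curve.** The event-free fraction before the window is S = 1 − F(1 − s), and q = Fs/S. The estimate at the end of the window is 1 − S × product of (1 − q/k), k = 1 to 7. At Day 253 the product uses k = 4 to 7.

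Worked case, F = 50% and s = 10%: S = 0.55 and q = 0.05/0.55 = 0.0909. The full product is 0.785, so the end of the curve reads 1 − 0.55 × 0.785 = 56.8%. At Day 253 the product is 0.933 and the curve reads 48.7%.

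| True CR by Week 37 | End of window, s = 5 / 10 / 20% | Day 253, s = 5 / 10 / 20% |
|---|---|---|
| 15% | 16.2 / 17.3 / 19.5 | 14.8 / 14.6 / 14.3 |
| 30% | 32.3 / 34.5 / 38.4 | 29.6 / 29.3 / 28.5 |
| 50% | 53.7 / 56.8 / 61.9 | 49.4 / 48.7 / 47.2 |
| 70% | 74.7 / 78.0 / 82.4 | 69.1 / 68.0 / 65.7 |

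The excess at the end of the window is 1.2 to 4.7 points for s = 5%, 2.3 to 8.0 for 10%, and 4.5 to 12.4 for 20%. At s = 5% it stays below 4 points for a true CR of 15% to 50%. The shortfall at Day 253 is 0.2 to 4.3 points.

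**Step 3: simulation, 4,000 trials per scenario.**
- Tail: with 60 per arm, F = 50% and s = 10%, the planned rule read 56.8% and a common censoring day 50.0%. With no visit spread the two agreed. With ±7 days the planned rule read 59.6%.
- Quartiles, 60 per arm: at F = 50% the 25th percentile never changed, and the median changed in 14% to 47% of trials. At F = 70% the median changed in under 1% and the 75th percentile in 24% to 68%.
- False median (the curve reaches 50% although fewer than half of the arm remitted), 60 per arm, as a share of all trials: under 1% at F = 15%; 2% to 12% at 30%; 12% and 22% at 40% for s = 5% and 10%.
- Log-rank test (unstratified, 60 per arm): type I error 4.6% to 5.3% as planned against 4.6% to 5.5% with a common day. Power for 50% against 30% was 59.0% to 59.5% against 59.1% to 61.1%.

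**The case against.** The strongest reply is that the endpoint is decided by the stratified log-rank test, which does not move, so only the display of one week of the curve is at issue. That is right about inference. It does not excuse reported estimates that disagree with the trial's own counts.

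Three further points stand in part.
- The event date also depends on when the CS dose first reaches 10 mg/day. Doses change weekly near that level, and unscheduled visits include an efficacy assessment. Some late events may therefore fall between visits, which reduces the bias. The public text of SAP 6.1.9 does not show the derivation in enough detail to settle this.
- The Week 37 share of first CRs is an assumption, and at a small share the error is small.
- The event count will be reported beside the curve, so a careful reader could recover the crude proportion.

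A reader might infer that all quartiles and the Week 37 landmark are wrong, or that a false median is common whenever fewer than half of an arm remits. The documents and the arithmetic do not support that. Quartiles reached before about Day 250 are right. SAP 8.2 does not say the landmark is read from the curve or on which day, and a plain proportion would be unaffected. False-median rates well above a quarter need a true CR near 50% or a large Week 37 share.

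**Conclusion.** The point holds for estimates read inside the Week 37 visit window: the end of the curve, any quartile that lies in the window or is pushed into it, and a landmark taken from the curve there. The bias is upward at the end of the window and slightly downward at Day 253. Table 4 fixes the mechanism; the sizes above rest on an even ±3-day spread, no drop-out and assumed Week 37 shares of 5% to 20%. Late visits would enlarge the bias, and events dated between visits would shrink it. A false median is a material risk mainly when an arm's true CR is about 40% to 50%.

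Patients who discontinue are also censored at an assessment date under Table 4, at earlier visits. The calculation does not cover them. This is a fault of estimation and presentation in a key secondary endpoint; it does not threaten the hierarchical test.

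**What to change.** Add one rule to Table 4, in either form:
- Censor every Week 37 completer without CR at one common administrative day, on or after the last blinded Week 37 reading in the trial, and read the landmark on that day. Reading it at Day 253 under this option would be too low (45.7% to 49.1% for a true 50%).
- Or give Week 37 events and censorings the target Day 253, with events counted before censorings on tied days as is usual, and read the landmark at Day 253.

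With complete follow-up, either option makes the estimate equal the plain proportion. Leave the rows for discontinuation, rituximab and death as they are. In SAP 8.2, state the landmark's method and reading day.

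The cost is a line in Table 4, a sentence in 8.2 and a small change to the derivation program. No new data are needed, and the formal test stays as specified.
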